6.2 Exclusion Criteria

6.2.1 Pre-screening Phase

The subject will be excluded from participating in the pre-screening phase if any of the following criteria are met:

- 1. Concomitant disease or condition that could interfere with the conduct of the study, or that would, in the opinion of the Investigator, pose an unacceptable risk to the subject in this study.
- 2. The subject has legal incapacity or limited legal capacity.
- 3. Significantly altered mental status that would limit the understanding or rendering of informed consent and compliance with the requirements of this protocol. Unwillingness or inability to comply with the study protocol for any reason.

6.2.2 Treatment Phase

The subject will be excluded from participating in the treatment phase if any of the following criteria are met:

- 1. Ongoing treatment with an anticancer agent not contemplated in this protocol.
- 2. Prior treatment (at least 1 full treatment cycle) with an FTase inhibitor.
- 3. Any history of clinically relevant coronary artery disease or myocardial infarction within the last 3 years, New York Heart Association (NYHA) grade III or greater congestive heart

failure, cerebro-vascular attack within the prior year, or current serious cardiac arrhythmia requiring medication except atrial fibrillation.

- 4. Known uncontrolled brain, leptomeningeal or epidural metastases (unless treated and well controlled for at least 4 weeks prior to Cycle 1 Day 1).
- 5. Non-tolerable ≥ Grade 2 neuropathy or evidence of emerging or rapidly progressing neurological symptoms within 4 weeks of Cycle 1 Day 1. Non-tolerable grade 2 toxicities are defined as those with moderate symptoms that the patient is not able to endure for the conduct of instrumental activities of daily life or that persists ≥ 7 days.
- 6. Major surgery, other than diagnostic surgery, within 4 weeks prior to Cycle 1 Day 1, without complete recovery.
- 7. Active, uncontrolled bacterial, viral, or fungal infections, requiring systemic therapy. Known infection with HIV, or an active infection with hepatitis B or hepatitis C.
- 8. Subjects who have exhibited allergic reactions to tipifarnib or structural compounds similar to tipifarnib or to the drug product excipients. This includes hypersensitivity to imidazoles, such as clotrimazole, ketoconazole, miconazole and others in this drug class. Patients with hypersensitivity to these agents will be excluded from enrolment.
- 9. Required use of concomitant medications classified as strong inhibitors or inducers of cytochrome P450 3A4 (CYP3A4, Table 4) or UDP-glucuronosyltransferase (UGT).
- 10. Concomitant disease or condition that could interfere with the conduct of the study, or that would, in the opinion of the Investigator, pose an unacceptable risk to the subject in this study.
- 11. The subject has legal incapacity or limited legal capacity.
- 12. Significantly altered mental status that would limit the understanding or rendering of informed consent and compliance with the requirements of this protocol. Unwillingness or inability to comply with the study protocol for any reason.

7 TRIAL DESIGN

7.1 Study Design

This Phase II study consists of 2 parts: 1) pre-screening phase and 2) treatment phase.

The pre-screening phase will investigate the presence of HRAS mutations in subjects with a histologically or cytologically confirmed diagnosis of squamous non-small cell lung cancer (SQ-

NSCLC). Subjects may participate in the pre-screening phase at initial diagnosis or following prior lines of therapy for SQ-NSCLC.

The treatment phase will investigate the antitumor activity in terms of ORR of tipifarnib in subjects with locally advanced squamous non-small cell lung cancer (SQ-NSCLC) with HRAS mutations and for whom there is no curative therapy available. Subject enrolment may proceed with information available on tumor HRAS status previously generated during the pre-screening phase of the study, but all subjects must consent to provide tumor slides (or tumor tissue block) from a prior diagnostic biopsy for a retrospective testing of RAS gene status, including T81C polymorphism, and other potential biomarkers at a central facility.

7.3 Assignment to Treatment Groups

This is a nonrandomized study. All eligible subjects enrolled in the treatment phase will be assigned to receive tipifarnib 600 mg to be taken orally with food bid for 7 days in alternating weeks (days 1-7 and days 15-21) in 28 day cycles.

7.4 Removal of Subjects from Treatment or Assessment

Subjects may withdraw their consent to participate in this study at any time without prejudice. The Investigator must withdraw from the study any subject who requests to be withdrawn. A subject's participation in the study may also be discontinued at any time at the discretion of the Investigator and in accordance with his/her clinical judgment. Every effort should be made to complete, whenever possible, the tests and evaluations listed for the End of Treatment visit. The Sponsor must be notified of all subject withdrawals as soon as possible. The Sponsor also reserves the right to discontinue the study at any time for either clinical research or administrative reasons and to discontinue participation by an individual Investigator or site for poor enrolment or noncompliance.

Overall, the reasons for which the Investigator or Sponsor may withdraw a subject from study treatment include, but are not limited to, the following:

- Subject experiences disease progression
- Subject experiences unacceptable toxicity
- Subject requires more than 2 dose reductions
- Subject experiences toxicity that is deemed by the Investigator to be no longer safe for the subject to continue therapy
- Subject requests to withdraw from the study treatment
- Subject requires or has taken medication prohibited by the protocol
- Subject is unwilling or unable to comply with the study requirements
- Subject withdraws consent to collect health information
- Subject was erroneously admitted into the study or does not meet entry criteria
- Subject is lost to follow-up
- Subject becomes pregnant

Subjects will return for an End of Treatment visit within approximately 30 days after the last administration of the study drug (or sooner if another anticancer therapy is to be initiated). If a subject fails to return for scheduled visits, a documented effort must be made to determine the reason. If the subject cannot be reached by telephone after 2 attempts, a certified letter should be sent to the subject (or the subject's legally authorized representative, if appropriate) requesting contact with the Investigator. This information should be recorded in the study records.

The Investigator must obtain documented consent from each potential subject prior to participating in a clinical trial. This trial has two consents forms, one per pre-screening phase and another per treatment phase.

Both consents must be documented by the subject's dated signature or by the subject's legally acceptable representative's dated signature on a consent form along with the dated signature of the person conducting the consent discussion.

A copy of the signed and dated consent form should be given to the subject before participation in the trial (both phases).

The initial informed consent forms, any subsequent revised written informed consent forms and any written information provided to the subject must receive the IRB/ERC's approval/favorable opinion in advance of use. The subject or his/her legally acceptable representative should be informed in a timely manner if new information becomes available that may be relevant to the subject's willingness to continue participation in the trial. The communication of this information will be provided and documented via a revised consent form or addendum to the original consent form that captures the subject's dated signature or by the subject's legally acceptable representative's dated signature.

Specifics about a trial and the trial population will be added to the consent form templates at the protocol level.

The informed consent forms will adhere to IRB/ERC requirements, applicable laws and regulations and Sponsor requirements.

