9.1 Efficacy Variables

Radiological and/or physical assessments of the tumor lesions will be made at screening (4 weeks before the first study drug administration), and approximately every 8 weeks for the first 6 months (cycles 2, 4, 6) and then every 12 weeks (cycles 9, 12, 15, etc.) until disease progression, starting at the end of Cycle 2. Additional tumor assessments may be conducted if deemed necessary by the Investigator or for a confirmation of an objective response. Subjects who discontinue treatment for reasons other than disease progression must continue tumor assessments until disease progression, withdrawal of their consent to study procedures or initiation of another anticancer therapy. Efficacy assessments may also be conducted at treatment discontinuation (End of Treatment visit) if the reason for the treatment termination is other than disease progression and a tumor assessment was not done within 8 weeks before

treatment discontinuation (assessment must be conducted before additional anti-tumor therapy is started). Scans at the End of Treatment visit will be also conducted if required to confirm response to treatment.

Lesions to be included in the tumor assessments should follow RECIST v1.1 criteria (Appendix II). Spiral CT scan with a contrast agent is the preferred imaging method. Tumor assessment with spiral CT scans of the abdomen, pelvis and chest plus other relevant evaluations, e.g. bone scans, should be performed as appropriate. Subjects with contrast allergy may use non-contrast CT or MRI, whichever is required to adequately assess all disease.

Objective response (complete response and partial response) as determined by the subject's best tumor response, duration of response, and time to progression will be assessed using RECIST criteria version 1.1. Confirmation of response is required.

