11.1 Populations

11.1.1 Efficacy Analysis

The FAS population will serve as the primary population for the analysis of tumor response and other efficacy-related data. Subjects will be excluded for FAS for the following reasons:

- No baseline data
- Failure to receive at least one dose of tipifarnib
- No post-baseline endpoint data subsequent to at least 1 dose of study drug

A supportive analysis using the Per-Protocol population will be performed for the tumor response analysis. The Per-Protocol population excludes subjects due to important deviations from the protocol that may substantially affect the results of the primary analysis, such as not taking at least 80% of the intended dose in cycle 1. The final determination on protocol violations, and thereby the composition of the Per-Protocol population, will be made prior to locking the clinical database and final analysis and will be documented in a separate memorandum.

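### Section 7.4 lets the Investigator end assessment as well as treatment, contrary to 9.1; combined with the FAS exclusion, this can raise the reported ORR

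*Combined protocol and SAP*

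**What the plan says.** **Leaving the study.** Section 7.4, whose title covers both treatment and assessment, states that a subject's "participation in the study may also be discontinued at any time at the discretion of the Investigator", a decision that is to rest on clinical judgment. A separate paragraph then lists reasons for withdrawing a subject from study treatment, so the discretionary clause is not simply another way of describing a stop to drug. For subjects who leave, 7.4 adds: "Every effort should be made to complete, whenever possible, the tests and evaluations listed for the End of Treatment visit". Every withdrawal is to be reported to the Sponsor.

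**Continuing scans.** Section 9.1 says that subjects who stop treatment without progression "must continue tumor assessments until disease progression, withdrawal of their consent to study procedures or initiation of another anticancer therapy". The synopsis has the same rule. Scheduled on-study scans run at intervals of about 8 weeks, "starting at the end of Cycle 2". Section 9.1 permits, but does not require, a scan at the End of Treatment visit when treatment stopped for a reason other than progression and none was done in the preceding 8 weeks.

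**Who is counted.** Section 11.1.1 states: "The FAS population will serve as the primary population for the analysis of tumor response and other efficacy-related data". One of its reasons for exclusion is "No post-baseline endpoint data subsequent to at least 1 dose of study drug". The synopsis (Statistical Methods) defines an evaluable subject for the two-stage design differently: tissue-confirmed HRAS missense mutation, a baseline scan and two doses. It asks for no post-baseline scan.

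**The concern.** A site could follow 7.4 and end all study procedures for a subject whom 9.1 says must still be scanned. The plan does not say which section governs.

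The timing matters. The first scheduled scan comes after two 28-day cycles, about week 8. The trial is open label and the Investigator determines response, so a discretionary exit before that scan may well follow clinical worsening. Such a subject would most likely have been a non-responder. If no scan is obtained on leaving, the FAS rule removes the subject from the ORR denominator, and the missing data then depend on outcome in a direction that favours the drug. With at most 18 subjects, one or two such losses visibly change the estimate and the p value.

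**Working it through.** **1. The plan's own design.** Inputs (Section 11.3): 7 subjects in stage 1, stop if 0 responses; 11 more in stage 2; success if at least 4 of 18 respond; null ORR 10%, alternative 30%.

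P(success) = Σ over x = 1 to 7 of P(X₁ = x; 7, p) × P(X₂ ≥ 4 − x; 11, p).

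- At p = 0.10: 0.0893 (stated 0.089).
- At p = 0.30: 0.800 (stated 80%).

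Both reproduce. These figures assume that all 18 evaluable subjects stay in the count.

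**2. One subject under each rule.** Take a subject with a tissue-confirmed mutation and a baseline scan who is dosed for some weeks and removed at the Investigator's discretion before week 8, with no scan on leaving.

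- Section 7.4: the exit is allowed.
- Section 9.1 and synopsis: scanning should have continued, as none of the three listed ends has occurred.
- Synopsis evaluable definition: the subject is in the denominator, without a response.
- Section 11.1.1 FAS: the subject is out of the denominator.

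**3. Effect on the ORR and its test.** The number k of early leavers is not given in the documents; it is assumed to run from 0 to 4. All leavers are taken to be non-responders and not replaced. ORR = R/(18 − k). The p value is the exact binomial test against 10% named in Section 11.2.1: P(X ≥ R; 18 − k, 0.10).

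| k | n | ORR, R = 4 | p, R = 4 | ORR, R = 3 | p, R = 3 |
|---|---|---|---|---|---|
| 0 | 18 | 22.2% | 0.098 | 16.7% | 0.266 |
| 1 | 17 | 23.5% | 0.083 | 17.6% | 0.238 |
| 2 | 16 | 25.0% | 0.068 | 18.8% | 0.211 |
| 4 | 14 | 28.6% | 0.044 | 21.4% | 0.158 |

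For R = 4, the 90% interval moves from 8.0%–43.9% (k = 0) to 9.0%–48.4% (k = 2). This assumes the Clopper-Pearson method, as Section 11.2.1 does not name one.

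With 4 responders, dropping one non-responder takes p from above to below the design level of 0.089. Section 11.2.1 sets no level for this test, and the p value ignores the two-stage structure, so the crossing is illustrative.

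**4. Effect on the decision rule.** Removing non-responders cannot change the number of responses. Without replacement, reaching 4 or more is unaffected. It changes only if leavers are dropped and replaced to reach 18. The contents list a Section 7.2 on replacement, but its text is not in the public document, so replacement is an assumption. If a share d of non-responders is lost this way, the apparent null rate is 0.10/(0.10 + 0.90 × (1 − d)):

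- d = 5%: 0.10/0.955 = 10.5%; chance of passing 0.102
- d = 10%: 0.10/0.91 = 11.0%; chance 0.117
- d = 20%: 0.10/0.82 = 12.2%; chance 0.154
- d = 30%: 0.10/0.73 = 13.7%; chance 0.207

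The design value is 0.089.

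**5. PFS and DOR.** The available text gives no censoring rule and no event rate, so no bias can be calculated.

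**The case against.** The strongest reply is that 7.4 is not the cause. A subject who leaves early and is counted as a non-responder adds no upward bias; the whole shift in step 3 comes from the FAS exclusion. That stands. A reader might infer that 7.4 by itself inflates the ORR, or that rewording it would cure the problem. Neither follows. A worsening subject can still reach week 8 without a scan through consent withdrawal, death, loss to follow-up or a new anticancer therapy, the last of which 9.1 expressly allows as an end to scanning.

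Second, 7.4 may be read as a general clause and 9.1 as the specific rule for subjects off treatment. The list in 9.1 is also not exhaustive in practice, since it omits death, loss to follow-up and study closure. This is a fair reading, but the text does not state it, and 7.4 speaks of participation in the study, separately from treatment.

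Third, there are safeguards: clinical judgment, best efforts at the End of Treatment visit, Sponsor notification, unscheduled assessments and a possible End of Treatment scan. They make a missing scan less likely. They do not rule it out, because the effort is qualified and the scan is optional.

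Fourth, a reader might infer that subjects removed later are censored for PFS and DOR at the point of worsening, biasing both upward. That is plausible, but the documents do not say it. Both endpoints are exploratory with summary statistics only, and Section 11 leaves detail of the primary and key secondary analyses to a SAP.

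**Conclusion.** The conflict between 7.4 and 9.1 is real and should be reconciled. Its statistical consequence is conditional: it needs an early exit without a scan and use of the FAS exclusion, which itself disagrees with the evaluable definition in the synopsis. Under those conditions, with 4 responders and 2 early leavers (an assumed number), the reported ORR rises by 2.8 percentage points (25.0% − 22.2%) and the exact p value falls by 0.030 (0.098 − 0.068).

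The documents do not support a claim that the go/no-go rule is inflated: without replacement it does not move, and with replacement the size depends on an unknown share of lost non-responders. How often such removals would occur is also unknown. The point merits a change because the remedy is nearly free and the trial is small, not because a large bias has been shown.

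**What to change.** 1. Reword 7.4 so that end of study treatment and end of assessment are separate. A subject taken off treatment at the Investigator's discretion stays under the tumor assessments in 9.1 and under survival follow-up. Section 9.1 starts survival follow-up at progression, so it should say explicitly that subjects who stopped earlier are included. Decisions about treatment itself are left as they are.
2. In 11.1.1, make the primary ORR denominator every dosed subject who meets the synopsis evaluable definition, and count those without a post-baseline scan as non-responders. This is the step that removes the bias, whatever the route of exit. It also keeps the analysis on the denominator for which the error rate of 0.089 and power of 80% were calculated.
3. State in the SAP how PFS and DOR treat a subject who leaves without documented progression.

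The cost is a few sentences. The scans are already required by 9.1, and survival information may be collected by phone. The downside is a slightly lower reported ORR when there are early leavers.

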7.5 Premature Discontinuation of the Trial

This trial may be discontinued prematurely in the event of any of the following:

 New information leading to a judgment of unfavorable risk-benefit of tipifarnib becomes available, e.g. due to: Evidence of inefficacy of tipifarnib in HRAS mutant tumors, occurrence of significant previously unknown adverse reactions or unexpectedly high intensity or incidence of previously known adverse reactions, or other unfavorable safety

findings in the HRAS mutant tumor patient population. Evidence of inefficacy may arise from this trial or from other trials; unfavorable safety findings may arise from clinical or non-clinical examinations, e.g. toxicology.

- Sponsor's decision that continuation of the trial is unjustifiable for medical or ethical reasons.
- Poor enrolment of subjects making completion of the trial within an acceptable time frame unlikely.
- Discontinuation of development of tipifarnib by the Sponsor.
- Request by a Health Authority.

Health Authorities and IRBs/IECs will be informed about the discontinuation of the trial in accordance with applicable regulations. In the case of premature discontinuation of the study, the investigations scheduled for the End of Treatment assessment should be performed and the appropriate eCRF section completed.

7.6 Definition of End of Study

For administrative and safety reporting purposes, the end of this clinical study is defined as the day when the last remaining study subject in the trial completes the last Follow-up assessment no later than 24 months after the last study subject is enrolled in the study. Provisions will be made for the continuation of study treatment in patients who demonstrate sustained objective response or disease stabilization and manageable toxicity beyond the end of the study, e.g. a single patient treatment protocol.

8 TREATMENTS

Subjects enrolled in the treatment phase will receive tipifarnib as monotherapy in this study. In the absence of unacceptable tipifarnib related emergent toxicity or disease progression, subjects may receive treatment with tipifarnib for up to 24 months at the discretion of the Investigator. Treatment beyond 24 months may continue upon agreement of the Investigator and the Sponsor. The Sponsor or its designee will provide the study site with a supply of tipifarnib sufficient for the completion of the study.

All study subjects will be also eligible to receive best supportive care (BSC) defined as any standard supportive measures that are not considered a primary treatment of the disease under study, including the use of growth factors (i.e. GCSF) for myelosuppression. BSC will be provided by the study sites.

8.1 Investigational Product (IP)

Tipifarnib is a small molecule being developed as a potent, selective inhibitor of FTase for the treatment of cancer and other malignancies.

8.1.1 **Product Characteristics**

Tipifarnib will be provided in bottles containing film-coated, compressed, oral tablet containing 100mg or 300mg of active substance. Each tablet strength has the same qualitative composition and a dose proportional quantitative composition. The tablets contain tipifarnib and the following inactive ingredients: lactose monohydrate, maize starch, hypromellose, microcrystalline cellulose, crospovidone, colloidal anhydrous silica, and magnesium stearate. The 100mg and 300mg tablets are white. The film coatings contain hypromellose, titanium dioxide, lactose monohydrate, polyethylene glycol, and triacetin. Further information can be obtained from the current version of the Investigator's Brochure.

8.1.2 Storage and Labeling

At a minimum, the label of each bottle of tipifarnib tablets shipped to the study sites will provide the following information: batch number/lot number, study identification, required storage conditions, directions for use, and country specific required caution statements.

Tipifarnib accountability records will be maintained by the pharmacy or designated drug preparation area at the study sites. Upon receipt of tipifarnib supplies, the pharmacist or designated study site investigational drug handler will inventory tipifarnib (separately for each strength, if applicable) and complete the designated section of the shipping form. The shipping/inventory form must be sent to the Fundación GECP monitor, as instructed.

Tipifarnib should be stored at controlled room temperature 15° C to 30° C. All study supplies must be kept in a restricted access area.

